the participant in advance of the informed assent discussion using REDCap's survey distribution tool. The eAssent form is designed to allow the participant to navigate forward and backward through the entire form and to access the form at a later time if desired. During the informed assent discussion, the potential participant's questions will be answered and at the end, the participant will verbally confirm they agree to be in the study. Because there can only be one signature ("certifier") for each REDCap eAssent form, there are separate REDCap eAonsent forms for the adolescent/young adult and the researcher presenting the form. The eAssent gives subjects the option to download a copy of the signed form. If a participant refuses or is unable to eAssent but is still interested in participating, a physical assent will be collected by the study team at the next inperson visit to the bariatric surgery center.

C. Study Design and Research Methods

Figure 1. Study Design

The pharmacotherapy group will receive oral phentermine and immediate release topiramate in combination, up-titrated to goal doses of 16mg and 100mg, respectively over 4 weeks*, then maintained at this dose for 8 additional weeks. Topiramate is gradually down-titrated during weeks 13 and 14 to prevent possible discontinuation symptoms.

Dosing Schedule^{†,§}

Uptitration:

- Week 1: 4mg phentermine + 25mg immediate release topiramate
- Week 2: 8mg phentermine + 50mg immediate release topiramate
- Week 3: 12mg phentermine + 75mg immediate release topiramate

Goal Dose:

- Weeks 4-12: 16mg phentermine + 100mg immediate release topiramate **Discontinuation (at study Visit 4)**:
- Week 13: Discontinue Phentermine + Decrease topiramate to 50mg
- Week 14: Decrease topiramate to 25mg for 7 days, then discontinue
- (*) Participants who do not tolerate goal doses will be maintained at the highest tolerated dose. (§) Per existing literature³⁴ and discussion with pharmacy, participants with moderate hepatic impairment (ALT >3x ULN but <10x ULN on two consecutive measures outside of acute illness, and no evidence of hepatic synthetic dysfunction), will follow the same dosing schedule, with doses reduced as needed

based on side effects (See Procedure for Study Drug Dose Reduction/Discontinuation).

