Nausea, Vomiting, Diarrhea	DSMP				
Rare, but Serious ⁴⁰					

Acute myopia, Secondary angle closure glaucoma	DSMP
Oligohidrosis, Hyperthermia	DSMP (including temperature at every study visit)
Metabolic acidosis	Bicarbonate at enrollment, visit 2, and visit 4
Suicidal ideation/attempt	DSMP with assessment at every study visit
Fetal toxicity	Pregnancy tests at enrollment and every study visit
(Pregnancy Risk Factor Category D- positive evidence of risk)	Requirement for females to either have a LARC (majority) or documented commitment to use 2 forms of birth control
Withdrawal symptoms	Gradual discontinuation at the end of the study
Hyperammonemia and encephalopathy	Drug interaction check; DSMP
Kidney stones	BMP at enrollment, visit 2, and visit 4; Drug interaction check; DSMP
Topiramate-Ethanol interaction (potential to cause increased CNS depression)	Counseling about alcohol avoidance, and specific language about this risk in the consent/assent

Methods for systematically assessing changes in mood, suicidality, and cognition.

Mood:

Changes in mood will be systematically screened for using the Center for Epidemiologic Studies Depression Scale (CES-D). This is a 20-item self-report questionnaire that covers areas including depressed mood, feelings of guilt/worthlessness, helplessness, psychomotor retardation, loss of appetite and sleep disturbance over the previous week. ⁴⁶ This instrument has yielded adequate internal reliability that is robust to age, clinical vs. nonclinical setting, and risk of bias. ⁴⁷ The original version of the measure is appropriate for individuals 12 years of age and older. The CES-D is routinely administered to individuals receiving care at the Children's Colorado Bariatric Surgery Center at every follow-up pre-operative and post-operative clinic appointment.

The proposed study will additionally administer the CES-D at all study visits not aligned with a clinical visit and will be scored by the PI or professional research assistant. A CES-D score <20 indicates no to mild depressive symptoms. And a CES-D score ≥20 indicates elevated depressive symptoms. This is based on a metaregression that supported higher cut points having better diagnostic accuracy.⁴⁷

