Any study participant who a) newly scores ≥20 at any time during the study or b) has a baseline score of ≥20 and who demonstrates any absolute increase in this score, compared to previous measures, will be discussed within 72 hours with the Bariatric Surgery Center's pediatric clinical psychologist to consider a more comprehensive follow-up clinical interview. The clinical interview will guide additional management recommendations, which may include psychoeducation on depression, a referral to therapy, a referral to psychiatry, and/or a reduction of study medication.

Weekly phone calls after study drug start also include a question about depressed mood over the previous week and if present, ask participants to rank this as mild, moderate, or severe. If depressed mood is present and moderate or severe, the PI will discuss follow-up steps with the participant and caregiver within 24 hours of identification after consulting with study psychologist [name]; If mild and new, the PI will discuss with study psychologist [name] within 1 week of identification.

Suicidality:

Suicidal ideation and behavior will be assessed using the Columbia Suicide Severity Rating Scale (C-SSRS)^{48,49} at enrollment and each study visit. Any participant who reports suicidal behavior or suicidal ideation with some intent to act (Type 4) or with intent and a specific plan (Type 5) during the study will be discussed with the PI during *that visit*. The PI will determine whether the participant should be escorted to the Children's Hospital Colorado Emergency Department for an emergent mental health evaluation or will be discussed within 72 hours with the Bariatric Surgery Center's pediatric clinical psychologist for additional assessment/treatment recommendations.

For both mood and suicidality, if a participant's psychiatric disorder can be adequately treated with psycho- and/or pharmacotherapy, then the patient, at the discretion of the mental health provider, should be continued in the trial on randomized therapy.

Cognition:

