- -Comprehensive review of systems at every study visit (to capture possible AEs not reported previously)
- -Physical exam at every study visit (e.g. new murmurs, rubs, or gallops, new increased work of breathing, new pulmonary edema, new peripheral edema);
- -Vitals at every study visit (e.g. new fever, tachycardia, new elevated blood pressure/hypertension)
- -Phone call 1, 2, and 3 weeks after study drug initiation and in-person with a questionnaire at visits 2, 3, and 4 to review known possible side effects of phentermine and topiramate
- -Lab monitoring: basic metabolic panel (to assess for new metabolic acidosis: bicarb < 18 mmol/L); urine pregnancy tests for all females at every visit.
- -Monitoring of mood, suicidality, and cognition per above with validated assessments at enrollment and every study visit (e.g. new or worsened depression, new suicidal ideation/behavior)
- -Between study visits, participants with questions about symptoms will also be encouraged to call the PI directly (voicemail messages are forwarded to the PI's password-protected email)
- 3. To what external entities will local adverse events be reported?: In addition to COMIRB, the PI will report local adverse events to the FDA, according to their safety reporting requirements: https://www.fda.gov/downloads/Drugs/Guidances/UCM227351.pdf). Specifically, the PI will report to the Division of Metabolism and Endocrinology within the FDA's Center for Drug Evaluation and Research, which reviewed the IND application for this study. The PI will report to this Division: 1) Any unexpected fatal or life-threatening suspected adverse reactions no later than 7 calendar days after initial receipt of the information, and 2) Any a) serious, unexpected suspected adverse reactions, b) findings from other clinical/animal/in-vitro studies

that suggest significant human risk, and c) a clinically important increase in the rate of serious suspected adverse reactions no later than 15 calendar days after determining that this information qualifies for reporting.

4. Will periodic global review of safety/adverse events (serious adverse events and adverse events) occur?: Yes, reviews will be performed by the PI, and a three-member data and safety monitoring board (DSMB), including a primary Safety Officer.

Reviewer	Expertise	Review Frequency	Written Reports	Report Frequency

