Route of Data Collection: To reduce in-person time on campus for participants, components of Study Visits 1-4 will be collected remotely (designated by superscript "R" in Table 3 below) either via secure video call or telephone call (with questionnaires emailed) in the participant's/guardian's preferred language within the same week and ideally on the same day as the study visit. These measures will be conducted remotely unless it is not possible or places an undue burden on the participant to do so (e.g. participant does not have a reliable internet connection or has a limited phone data plan that incurs significant charges). Pill count will require a video connection. All other measures require in-person collection/administration to appropriately collect outcome/safety data.

Table 3. Schedule of Measures

"X"= Study specific "O"= Standard of Care #= Bariatric Clinic or CHCO CTRC ‡= + Adult CTRC or CHCO Radiology/CTRC R= can be delivered remotely	SCREENING/ ENROLLMENT# 6-12 mo post- op	STUDY VISIT 1#,‡ ~1wk after Enrollment	STUDY VISIT 2# 4wks after Visit 1	STUDY VISIT 3# 4 wks after Visit 2	STUDY VISIT 4#,‡ 4 wks after Visit 3
Review of Inclusion/Exclusion criteria	Х				
Echocardiogram (ONLY for those with Hypertension or Severe OSA with poor PAP adherence IF not obtained in the prior 6 months)	0				
Demographics Form		X ^R			
Feasibility of protocol implementation (e.g. enrollment rates, dropout rates)	х	х	X	х	X
Study medication adherence & tolerability- Study Med Form			X ^R	X ^R	X ^R
Study medication adherence- (pill count)- Study Med Form			X ^R	X ^R	X ^R
Study medication adherence (urine amphetamine screen)		X	X	X	X
Review of all non-study medications (self-report)	Х	X ^R	X ^R	XR	X ^R
Patient/family satisfaction survey					X ^R
Weight, Height, Temperature, HR, BP; Review of Systems; Physical exam		X	Х	X	X
Urine pregnancy test	X	X	X	X	X
Lipid panel, ALT, HbA1c	Х				Х
Basic metabolic panel	Х		Х		X
Optional Biobanking	Х		Х		X
3-day diet record review		X ^R			X ^R
Previous Day Physical Activity Recall (PDPAR)		X ^R			X ^R

IWQOL-Kids (≤19yo)/-Lite (≥ 20yo) & Parent Report		X ^R			X ^R
PedsQL (general health-related quality of life)		X ^R			X ^R
CES-D (Depression Screen)	0	X	X	Χ	X
C-SSRS (Suicide Screen)	X	X	X	Х	X
Resting metabolic rate		X			X
DEXA-3 site		X			Х
Clinical Intervention/Translation Core: Eating behavior questionnaires (VAS, TFEQ, EAH)		X ^R	X ^R	X ^R	X ^R

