In addition to the above in-person study visits and designated remote data collection, there are eight standard study phone calls in the protocol:

- Phone Call 1: 1-2 days before the Screening/Enrollment Visit 0 (Reminder to fast)
- Phone Call 2: 1 week before Visit 1 (Phone Call Script 1)
- Phone Call 3: 1 week after Visit 1 (Phone Call Script 2)
- Phone Call 4: 2 weeks after Visit 1 (Phone Call Script 2)
- Phone Call 5: 3 weeks after Visit 1 and 1 week before Visit 2 (Phone Call Scripts 1 & 2)
- Phone Call 6: 1 week before Visit 3 (Phone Call Script 1)
- Phone Call 7: 1 week before Visit 4 (Phone Call Script 1)
- Phone Call 8: 1 week after last dose of study drug (Phone Call Script 2)

If a participant requires additional dose titration during the protocol, the PI will conduct additional weekly phone calls until study medication dosage is stable.

E. Potential Scientific Problems:

Benchmarks for success, pitfalls, and alternatives:

Primarily, we expect this protocol to demonstrate feasibility, which will form the foundation for a larger study of pharmacotherapy as an adjunct to bariatric surgery. Secondarily, we expect to demonstrate short-term efficacy of pharmacotherapy in terms of promoting additional weight loss and improving biological markers.

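### No contact is scheduled during the two topiramate step-down weeks, and the one-week mood question reused at Call 8 would not reach back to them

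*Combined protocol and SAP*

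**What the plan says.** The Dosing Schedule in Section IV.C places stopping under the heading "Discontinuation (at study Visit 4"), with the first step "Week 13: Discontinue Phentermine + Decrease topiramate to 50mg". It gives the reason for the step-down: "Topiramate is gradually down-titrated during weeks 13 and 14 to prevent possible discontinuation symptoms".

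Table 2, in the topiramate part, lists withdrawal symptoms among the rare but serious reactions. Its whole mitigation entry is "Gradual discontinuation at the end of the study". No monitoring is named in that row.

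Table 3 sets Visit 4 at "4 wks after Visit 3" and has no later column. The CES-D, the C-SSRS, the review of systems and the tolerability form are therefore not scheduled after Visit 4.

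Of the eight standard calls listed below Table 3, one follows Visit 4: "Phone Call 8: 1 week after last dose of study drug (Phone Call Script 2"). Script 2 is also the script for Calls 3, 4 and 5, made one, two and three weeks after Visit 1.

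The Mood subsection of Section IV.D says: "Weekly phone calls after study drug start also include a question about depressed mood over the previous week". The list of ways to identify adverse events in item 2 of the Data and Safety Monitoring Plan gives "Phone call 1, 2, and 3 weeks after study drug initiation and in-person with a questionnaire at visits 2, 3, and 4" for the review of known side effects. It does not mention Call 8.

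**The concern.** A one-week recall suits calls made a week apart, as during up-titration. Call 8 comes three weeks after the last scheduled contact, so the same question leaves the first two of those weeks uncovered. They are the weeks in which topiramate is being reduced, and the plan itself gives avoidance of discontinuation symptoms as the reason for reducing it gradually.

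A low mood that began and settled during the step-down could be missed by this question unless the participant volunteered it. The stake is the completeness of the descriptive safety information on how treatment ends, in a pilot meant to prepare a larger study.

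**Working it through.** The plan gives no figure of its own for this, so the check is calendar arithmetic. Day 1 is the first dose at Visit 1, and week w covers days 7(w − 1) + 1 to 7w.

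**Inputs**
- Visits 2, 3 and 4 each follow the preceding visit by 4 weeks (Table 3).
- The goal dose runs through weeks 4 to 12 and the topiramate step-down through weeks 13 and 14 (Section IV.C).
- Call 8 is 1 week after the last dose (list of standard calls).
- The mood question looks back 1 week (Section IV.D, Mood).

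**Timeline**
- Visit 4: 4 + 4 + 4 = 12 weeks, day 84.
- Check: weeks 4 to 12 are 12 − 4 + 1 = 9 weeks at goal dose, which agrees with the 9 weeks stated under Pitfalls in Section IV.E.
- Week 13 is days 85 to 91 and week 14 is days 92 to 98, so there are 14 step-down days and the last topiramate dose is about day 98.
- Call 8: 98 + 7 = day 105, the end of week 15.
- Gap from Visit 4 to Call 8: 105 − 84 = 21 days.

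**What the mood question reaches at Call 8**

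| Counting of the look-back | Days covered | Step-down days covered |
|---|---|---|
| 7 days ending on the day of the call | 99 to 105 | 0 of 14 |
| 7 days before the day of the call | 98 to 104 | 1 of 14 |

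Either way the look-back is 7 of 21 days, or 33%.

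**Sensitivity to the length of the look-back** (days before the day of the call)
- 14 days: days 91 to 104, which covers 8 of the 14 step-down days.
- 21 days: days 84 to 104, which covers all 14.

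**Sensitivity to the meaning of last dose.** Topiramate is the drug taken last, so day 98 is the natural reading. If the phrase meant the last phentermine dose (day 84), the call would fall on day 91. A 7-day look-back ending that day would cover week 13, 7 of the 14 step-down days, and no scheduled contact would follow week 14.

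**The case against.** The strongest objection is that the gap is shown for one question only. The one-week recall is stated for depressed mood, and for the weekly calls; Call 8 is not one of a weekly series. Script 2 is not in the document. The self-report adverse-effect checklist described under Cognition has no stated recall period. If Script 2 carries a side-effect review of that kind, Call 8 could pick up symptoms from weeks 13 and 14. This stands. A reader might infer that the step-down weeks are never asked about; the documents do not support that, and do not exclude it either.

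A reader might also infer that Call 8 is the only contact of any kind. It is the only scheduled one. The Data and Safety Monitoring Plan encourages participants with questions about symptoms to call the investigator between visits, and weekly calls are added when further titration is needed. Whether a step-down planned for everyone counts as further titration is unclear. Routine clinic care does not clearly fill the gap: for those enrolled at 6 or 9 months, Visit 4 typically is the next postoperative clinic visit.

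A third tempting reading is that the plan names a withdrawal window covering both drugs. It does not. Discontinuation symptoms are mentioned generically, without a time window and without mood, and for topiramate only. For phentermine, Table 2 says that clear evidence of withdrawal is lacking. Call 8 does cover the first week off topiramate.

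Finally, the absence of Call 8 from the list for identifying adverse events has little consequence. The same item requires a form for any event reported or elicited during the study, so adding the call would be editorial. Nor does a planned estimate change: the tolerability rate in the sample size section counts participants who do not stop medication because of adverse effects.

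What remains is that a question designed for weekly calls is apparently reused after a three-week gap, and that the recall period of the other questions at Call 8 is unstated.

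**Conclusion.** The point holds as a minor one. No study contact is scheduled in about days 85 to 98. The mood question at the single scheduled contact afterwards would reach 0 or 1 of the 14 step-down days and 7 of the 21 days since Visit 4. Table 2 assigns no monitoring to topiramate withdrawal symptoms.

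This rests on three assumptions: that Script 2 keeps the one-week mood recall at Call 8, that last dose means the last topiramate dose, and that the participant follows the nominal schedule. If Script 2 already asks about the whole period since Visit 4, the sponsor need only say so. The documents do not support the conclusion that discontinuation symptoms go unasked, or that the stopping phase is unmonitored.

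**What to change.** For Call 8 only, set the recall period of the mood question and of the side-effect review to *since Visit 4*, and record onset and resolution dates so that events can be placed within or after the step-down. State this where the standard calls are listed.

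The cost is a small change to the script for one call. No call, visit or staff time is scheduled in addition, and no dose, step-down schedule or stopping rule changes. The downside is that recall over three weeks is somewhat less accurate than over one. Naming Call 8 in the list for identifying adverse events would be a tidy editorial addition, and a separate by-arm table of events after Visit 4 is a matter of preference; neither is needed to close the gap.

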Unpublished latent class growth trajectory modeling data from our group of the Teen-LABS³² participants 5 years after Roux-en-Y Gastric Bypass (RYGB) or Sleeve Gastrectomy (SG) demonstrate significant heterogeneity in surgical response. Where ≥ 20% BMI loss is considered to be an adequate response, among adolescents who had RYGB, 16% achieved only a 5% BMI loss and another 21% achieved a 16% BMI loss at 5 years. Among those who had SG, 36% achieved only a 7% BMI loss at 5 years postoperatively. Additionally, greater %BMI loss at 6 months postoperatively was associated with a more successful 5-year BMI trajectory. These data further underscore the need for adjunct treatment options for a sizeable subset of adolescents within the first year after bariatric surgery.

The Bariatric Surgery Center at Children's Hospital Colorado³³, led by Drs. [name] (Surgical Director) and [name] (Medical Director), began seeing patients in June 2017. Patients undergo either SG or RYGB. Over the last 25 months, patient volume has accelerated, and currently there are 103 patients in the program (Mean age: 17 [Range: 10-36]; Female: 73%; Race/Ethnicity: 46% Hispanic, 27% Non-Hispanic White, 14% Black, 13% Other). Based on a chart review of current postoperative patients who have had surgery ≥6 months ago, we estimate that 2 patients per month will meet inclusion criteria for this study. Therefore, we anticipate that 14 patients will be eligible for enrollment during the proposed 7-month recruitment timeline (Table 2). This allows for a 29% reduction in eligible individuals from the combination of upfront decline and dropout to successfully meet the target sample size of 10. This does not account for projected increases in overall Bariatric Surgery Clinic patient volume over the proposed timeline.

The patented combination pill phentermine/topiramate XR (trade name Qsymia) is generally not covered by Colorado insurance plans and costs ~\$200/month out of pocket, which makes it inaccessible for the vast majority of our patient population. We, like other pediatric weight management programs, prescribe phentermine and *immediate release* topiramate as individual medications (~\$30/month). This research proposal was designed to mimic this usual practice of prescribing individual phentermine and immediate release topiramate pills, which will allow for a more realistic assessment of feasibility and increases generalizability.

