Fourteen patients (7/arm) followed in the Children's Hospital Colorado Bariatric Surgery Center who meet inclusion criteria: 12-24yo; s/p SG or RYGB; and at 6-12 months post bariatric surgery^a, have either a) not achieved mean expected weight loss based on national standards and still have at least class 1 obesity or b) remain severely obese (\geq 120% of 95%ile or BMI \geq 35kg/m2 for 12-17yo; BMI \geq 35kg/m2 for 18-24yo) will be randomized 1:1 to pharmacotherapy + SOC^b or placebo + SOC in double-blind fashion. Expected weight loss at 6, 9, and 12 months postoperatively will be defined as a \geq 26%, \geq 28%, and \geq 31% decrease in weight, respectively, from preoperative weight (within 1 week of surgery) as was observed in the Teen-LABS study.⁷

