Sample size justification: Based on recommended practice for pilot studies, 60 the minimum sample size (10 total participants, 5 per arm) is driven by the primary aim of the study and represents a balance between participant availability (patient volume and recruitment timeline), and acceptable precision around feasibility estimates (Aim 1), which will be used for subsequent study planning. It is not based on a power calculation for group differences seen in any Aim 2 or 3 measures. To estimate precision around dropout and medication tolerability rates, we used a confidence interval approach with normal approximation of the binomial calculation 60-62. First, we estimate that a realistic dropout rate is 25%, based on 3 prior anti-obesity medication RCTs conducted in obese adolescents. 22,63,64 A realistic medication tolerability rate (% who do not discontinue medication because of adverse effects) is 85%, based on the single RCT of topiramate in adolescents and two larger RCTs of phentermine/topiramate XR in adults. ^{22,65,66} Dropout: With the minimum of 10 adolescent/young adult participants, if our observed dropout rate is 25%, we can be 68% confident that the enrollment rate estimate is accurate within 13 percentage points (or 90% confident that it is accurate within 20%). With 14 adolescent/young adult participants, if our observed dropout rate is 25%, we can be 68% confident that the enrollment rate estimate is accurate within 11 percentage points (or 90% confident that it is accurate within 18%). Medication tolerability: With 10 adolescent/voung adult participants, if our observed medication tolerability rate is 85%, we can be 68% confident that the tolerability estimate is accurate within 9 percentage points (or 90% confident that it is accurate within 16%). With 14 adolescent/young adult participants, if our observed medication tolerability rate is 85%, we can be 68% confident that the tolerability estimate is accurate within 9 percentage points (or 90% confident that it is accurate within 15%). Given possible constraints around enrollment, the level of precision with 10 or 14 adolescents/young adults was deemed acceptable to achieve protocol refinement for future RCT development.

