Planned analyses: Descriptive statistics will characterize the study population. Independent samples t-tests will be performed for continuous variables and chi-square for categorical variables to determine statistically significant differences between experimental and control groups. Aim 1: Feasibility of acceptability (adherence, tolerability, and satisfaction) will be descriptively assessed using differences in proportions between experimental and control groups. Feasibility of protocol implementation will be established by determining the proportions (rates) of recruitment, enrollment, randomization, and dropout. Aims 2,3: Estimated means and variability of continuous health outcome variables (e.g. % change in weight) and intra- and intersubject variability of repeated measures (e.g. loss of control eating) will be graphically presented and visually compared for experimental vs. control groups, as this aim is not powered to run inferential statistics.

G. Summarize Knowledge to be Gained:

The goal of this study is to establish the feasibility and initial efficacy of two common anti-obesity medications for adolescents who require additional risk reduction following bariatric surgery.

Adolescents with severe obesity who don't achieve optimal weight loss and co-morbidity improvement after bariatric surgery have few evidence-based treatment options to mitigate significant health risks through the remainder of adulthood. This study has the potential for substantial impact regardless of results, given that anti-obesity medications are currently being used in the post bariatric surgery setting without an evidence base. A recent international pediatric obesity webinar (4/2019) with contributors from leading adolescent bariatric surgery centers strongly expressed need and enthusiasm for studying the role of pharmacotherapy after surgery. Our center's volume, interdisciplinary expertise, and existing IND to study these medications in this setting sets us apart as the best positioned adolescent bariatric surgery center to carry out this initial pilot, with high potential for a subsequent larger multi-site RCT to evaluate safety and efficacy, mechanism of action, and predictors of response.

H. References:

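### Four of the eight Aim 1 precision margins are too small by the plan's own method, and tolerability precision is given only for drug and placebo arms pooled

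*Combined protocol and SAP*

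**What the plan says.** Section IV.F, Sample size justification, explains the planned size as follows: "minimum sample size (10 total participants, 5 per arm) is driven by the primary aim of the study and represents a balance". The two considerations weighed are how many patients can be recruited and how precise the feasibility estimates will be. It names the method, a normal-approximation confidence interval for a binomial proportion, and assumes observed rates of 25% for dropout and 85% for medication tolerability. Tolerability is the share who do not stop medication because of adverse effects.

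It then prints eight margins, at 68% and 90% confidence:

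- Dropout, N=10: "enrollment rate estimate is accurate within 13 percentage points (or 90% confident that it is accurate within 20" points.
- Dropout, N=14: "enrollment rate estimate is accurate within 11 percentage points (or 90% confident that it is accurate within 18" points.
- Tolerability, N=10: "tolerability estimate is accurate within 9 percentage points (or 90% confident that it is accurate within 16" points.
- Tolerability, N=14: 9 points at 68% and 15 at 90%.

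The tolerability rate "is 85%, based on the single RCT of topiramate in adolescents and two larger RCTs of phentermine/topiramate XR in adults". Section IV.B says that 14 patients, 7 per arm, "will be randomized 1:1 to pharmacotherapy" or placebo, each with standard of care. Under Planned analyses in Section IV.F, the Aim 1 acceptability measures, including tolerability, "will be descriptively assessed using differences in proportions between experimental and control groups". On availability, Section III says "we anticipate that 14 patients will be eligible for enrollment during the proposed 7-month recruitment timeline".

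**The concern.** Method, rates, sample sizes and confidence levels are all stated, so the margins should reproduce. One inconsistency shows before any calculation. The 68% tolerability margin is 9 points at both N=10 and N=14 for the same observed 85%. Under the normal approximation the first must be √(14/10) = 1.18 times the second. Two numbers that both round to 9 differ by a factor of at most 9.5/8.5 = 1.12, and two that both truncate to 9 by less than 10/9 = 1.11.

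The second issue is the population. Tolerating the drugs can be observed only in people who take them, and under 1:1 allocation that is half the sample. A rate from active-drug trials, applied to both arms together, gives a margin for a quantity that the planned by-arm analysis does not report.

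These margins are the plan's only quantitative precision argument for its size. The plan judges that precision sufficient and intends the feasibility estimates to inform a later trial. A reader relying on the printed figures would think active-drug tolerability better known than it will be. No decision or stopping rule depends on the margins.

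**Working it through.** **Inputs.** From Section IV.F: p = 0.25 (dropout), p = 0.85 (tolerability), N = 10 or 14, two-sided 68% and 90% confidence. From Sections IV.F and IV.B: 5 or 7 per arm.

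**Formula.** Margin = z × √(p(1−p)/n), with z = 0.9945 (68%) and 1.6449 (90%).

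**Step 1: the eight printed margins (percentage points).**

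| Quantity | N | Level | Printed | Recomputed | Shortfall |
|---|---|---|---|---|---|
| Dropout 25% | 10 | 68% | 13 | 13.62 | 0.6 |
| Dropout 25% | 10 | 90% | 20 | 22.52 | **2.5** |
| Dropout 25% | 14 | 68% | 11 | 11.51 | 0.5 |
| Dropout 25% | 14 | 90% | 18 | 19.04 | **1.04** |
| Tolerability 85% | 10 | 68% | 9 | 11.23 | **2.2** |
| Tolerability 85% | 10 | 90% | 16 | 18.57 | **2.6** |
| Tolerability 85% | 14 | 68% | 9 | 9.49 | 0.5 |
| Tolerability 85% | 14 | 90% | 15 | 15.70 | 0.7 |

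Example: 1.6449 × √(0.85 × 0.15/10) = 1.6449 × 0.1129 = 0.1857.

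Four margins are short by more than 1 point, so even cutting off decimals does not explain them. At the stated rates these four carry, in table order, about 86%, 88%, 57% and 84% confidence instead of 90%, 90%, 68% and 90%. The count of four is lenient: with ordinary rounding, seven of the eight are too small and only the N=14, 68% tolerability margin is right.

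**Step 2: other methods.** At the stated rates, Wilson intervals come within 0.7 point of the dropout margins but still give 11.2/18.1 for tolerability at N=10. Agresti–Coull intervals also exceed both N=10 tolerability margins. Continuity-corrected and exact intervals are wider than every printed margin.

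**Step 3: tolerability on active drug at 85%.**

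| Active arm | 68% | 90% | Printed for the pooled total | Ratio to printed |
|---|---|---|---|---|
| n = 5 (of 10) | 15.88 | 26.27 | 9 / 16 | 1.76 / 1.64 |
| n = 7 (of 14) | 13.42 | 22.20 | 9 / 15 | 1.49 / 1.48 |

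Halving the sample alone multiplies a margin by √2 = 1.41. The rest of each ratio is the shortfall from Step 1; for example, 11.23/9 = 1.25 and 1.41 × 1.25 = 1.76.

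**Step 4: does the normal approximation hold at these sizes?** Sum the binomial probabilities at a true 85% over the counts whose nominal 90% normal interval contains 0.85. Coverage is 88.6% (n=14), 79.3% (n=10), 66.7% (n=7) and 53.0% (n=5). The main reason is that when everyone tolerates the drug the interval has zero width and misses. That happens with probability 0.85⁷ = 0.32 at n=7 and 0.85⁵ = 0.44 at n=5.

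For scale, the 90% intervals for possible active-arm results are:

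- 6 of 7: exact 48% to 99%; Wilson 55% to 97%.
- 4 of 5: exact 34% to 99%; Wilson 44% to 95%.

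**Step 5: the between-arm difference.** The plan states no placebo tolerability rate, so one has to be assumed. The 90% margin is 1.6449 × √(0.85 × 0.15/n + q(1−q)/n), where q is the placebo rate:

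| Assumed q | 5 per arm | 7 per arm |
|---|---|---|
| 85% | 37 | 31 |
| 95% | 31 | 26 |

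Section II cites an odds ratio of 2.32 against placebo for stopping because of adverse events in adults. With 85% on active drug this implies placebo odds of stopping of (0.15/0.85)/2.32 = 0.076, or about 93% tolerability, inside that range.

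**The case against.** The best defence of the printed figures is that 25% of 10 or 14 and 85% of 10 are not whole people. The normal approximation at 2/10, 3/14, 9/10 and 12/14 gives 12.6/20.8, 10.9/18.0, 9.4/15.6 and 9.3/15.4. Rounded, these match seven of the eight printed margins; only 20.8 against 20 does not. This is a plausible origin, but it is an inference because the plan states no counts. Those counts are rates of 20%, 21.4%, 90% and 85.7%, whereas the sentences say 25% and 85%, so they remain wrong as written.

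It can also be said that pooling is not an arithmetic error, that the per-arm sizes are disclosed, and that a later trial would use observed rates by arm rather than these planning margins. Pooling is appropriate for dropout, and the reader can work out the arm sizes. But the paragraph's purpose is to show the precision to be expected, and it shows none for the people who take the drugs.

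Finally, the pooled shortfalls are small, the study is an unpowered pilot, and patient availability also sets its size. All true, and this limits the consequence to how precision is described.

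**Conclusion.** The point holds. By the stated method four of the eight margins are too small, by 1.0 to 2.6 points; the dropout margin at N=14 and 90% is the marginal case. This rests only on the plan's own inputs and a two-sided reading of the confidence levels.

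The denominator matters more. At the assumed 85%, active-drug tolerability would be known to within about 22 points (n=7) or 26 points (n=5) at nominal 90%, against a printed 15 or 16, and the normal interval is unreliable at those sizes. The approximation is close to nominal only for the planned pooled N=14.

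The dropout sentences also name the wrong quantity: enrollment and dropout are separate Aim 1 measures in Section IV.A. The paragraph should be corrected, but the pilot's design and feasibility aim are not undermined.

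**What to change.** Rewrite the precision paragraph in Section IV.F:

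1. Restate all eight margins to one decimal under a single rounding rule (68%/90%). Dropout: 13.6/22.5 (N=10) and 11.5/19.0 (N=14). Tolerability: 11.2/18.6 (N=10) and 9.5/15.7 (N=14). If whole-number counts were intended, state the counts and the rates they imply.
2. Add tolerability precision for the active arm, n=5 and n=7, and make it the figure that supports the tolerability objective. Keep the pooled denominator for dropout.
3. Use Wilson or exact intervals for per-arm rates, in planning and in reporting, and preferably for the pooled minimum of 10, where coverage is 79.3%.
4. Call the quantity in both dropout sentences the dropout rate.
5. Optionally, give a margin for the between-arm difference, with the placebo rate labelled as an assumption and a range shown.

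The cost is rewording one paragraph. The stated precision becomes less favourable, so the statement that it is sufficient should be reconsidered against the new figures. Enrolment and conduct do not change.
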